5 AMENDMENTS AND UPDATES

DOCUMENT HISTORY

Number	Date	Section of study protocol	Amendment or update	Reason
1	31 May 2023	Refer to protocol amendment	Amendment	Refer to protocol amendment summary of
		summary of changes		changes

AMENDED PROTOCOL 1 (31 MAY 2023)

This amended protocol (amendment 1) is considered to be nonsubstantial based on the criteria set forth in Article 10(a) of Directive 2001/20/EC of the European Parliament and the Council of the European Union as well as the Medicines for Human Use (Clinical Trials) Regulations 2004 in the UK. This is because it does not significantly impact the safety or physical/mental integrity of participants, nor the scientific value of the study.

OVERALL RATIONALE FOR THE AMENDMENT

As stated in the study protocol v2.0, a minimal sample size of 150 vaccinees (an 8% precision) would be targeted assuming an expected proportion of interest of 50%. The vaccinee questionnaire collection started on 16 March 2023. As of 24 May 2023, only 9 vaccinees completed questionnaires within 2 months of vaccinee data collection, although 123 vaccinees clicked the survery link based on IQVIA tracking. According to some HCPs who agreed to distribute the survey flyers to vaccinees, there are three possible explanations for the extremely low response rate among vaccinees:

- Difficulty to follow up with vaccinees because HCPs do not see vaccinees after yellow fever vaccination
- Vaccinees lost interest in participation when they realize they would not receive an honorarium
- Vaccination on-demand varies and low season for yellow fever vaccination

For the vaccinee survey, the primary objective is "To verify the receipt of the STAMARIL® PIL by yellow fever vaccinees at the time they get vaccination consultation in the UK", and the secondary objective is "To evaluate the yellow fever vaccinees' knowledge and understanding of the key safety messages in the STAMARIL® PIL in the UK". To increase the response rate among vaccinees, the MAH will remove secondary objective, amend the study protocol on conducting and reporting this survery according to the rationale summarized in the table below, and in line with the following plan:

• Shorten the vaccinee questionnaire by removing four questions designed for secondary objective

31-May-2023

Version number: 3.0

Provide an honorarium to each vaccinee who participate in the survey

Section # and Name	Description of Changes	Brief Rationale
PASS Information	Added EU PAS register number: EUPAS50782; Added "None" after "Secondary objective:" and deleted "1. To evaluate the yellow fever vaccinees' knowledge and understanding of the key safety messages in the STAMARIL® PIL in the UK."	The study was registered at ENCePP website on 22 February 2023 before questionnaire collection. Remove secondary objective in order to shorten vaccinee questionnaire to decrease the time to completion.
Section 3: Responsible parties	Name and email updated in Sanofi team	The names and emails are updated for Global Safety Officer and Statistician.
Section 4: Abstract (Research question and objectives)	Deleted "The secondary objective of this study is: 1. To evaluate the yellow fever vaccinees' knowledge and understanding of the key safety messages in the STAMARIL® PIL in the UK." Updated as "There is no secondary objective."	Shorten vaccinee questionnaire to decrease the time to completion.
Section 4: Abstract (Vaccinee questionnaire)	Deleted "• Variables related to the knowledge and understanding of the key safety messages in the STAMARIL® PIL (including risk factors and awareness of serious adverse reactions)"	Shorten vaccinee questionnaire by removing variables related to secondary objective to decrease the time to completion.
Section 4: Abstract (Data sources)	The sentence "Each questionnaire is estimated to take 10 to 15 minutes to complete" is changed to "It is estimated to take 10 to 15 minutes to complete HCP questionnaire, and up to 5 minutes to complete vaccinee questionnaire".	Update the time for a vaccinee to complete the shortened questionnaire.
Section 4: Abstract (Milestones)	Study milestones updated.	The end of data collection and the final study report submission are updated based on up to 24-week of data collection period.

Section 5: Amendments and updates	Deleted the words "None" and "Not applicable". Section was written as per amendment instructions in the template i.e., document history, and rationale for amending the protocol.	Because of very low response rate for vaccinee survey after two months of data collection, the MAH plans to shorten vaccinee questionnaire to decrease the time to completion and provide an honorariumto each vaccinee to motivate them to participate in the survey.
Section 6: Milestones	The words "After MHRA approval and before start of data collection" are changed to "February 2023 (actual)". Study milestones updated.	The study was registered at ENCePP website on 22 February 2023 before questionnaire collection. The start of data collection date was updated from planned date to actual date.
		The end of data collection and the final report of study results are updated based on up to 24-week of data collection period.
Section 8: Research question and objectives (Table 1)	Added "None" after "Secondary objective:"; Deleted "1. To evaluate the yellow fever vaccinees' knowledge and understanding of the key safety messages in the STAMARIL® PIL in the UK." and the related endpoints.	Remove secondary objective in order to shorten vaccinee questionnaire to decrease the time to completion.
Section 9.2.4.2: Vaccinee selection	Changed the sentence "Likewise, there will be no incentive for the vaccinees, which might otherwise cause them to worry about the answer they provide about the use of the checklist by their HCPs" to "There will be incentive for the vaccinees. As there will be no information linking the vaccinees' identities with the recruiting HCP, vaccinees will be unlikely to worry about the answer they provide about the use of the checklist by their HCPs."	The MAH plans to provide an honorarium to each vaccinee to motivate them to participate in the survey.

Section 9.3.2: Vaccinee questionnaire	Deleted "• Variables related to the knowledge and understanding of the key safety messages in the STAMARIL® PIL (including risk factors and awareness of serious adverse reactions)."	Shorten vaccinee questionnaire by removing variables related to secondary objective to decrease the time to completion.
Section 9.4.1 Questionnaire description (Vaccinee questionnaire will include questions on)	Deleted "• knowledge and understanding of the key safety messages in the STAMARIL® PIL"	Shorten vaccinee questionnaire by removing the questions designed for secondary objective to decrease the time to completion.
Section 9.4.3 Time to completion	Changed the word "Each" to "HCP". Added the sentence "Vaccinee questionnaire is estimated to take up to 5 minutes to complete."	Update the time for a vaccinee to complete the shortened questionnaire.
Section 9.4.4 Approaches for increasing response rate	Added "and an honorariumafter they complete the survey" at the end of this section.	The MAH plans to provide an honorarium to each vaccinee to motivate them to participate in the survey.
Section 9.5.2 Sample size feasibility	The number of vaccinees possible to recruit assuming 160,000 or 46,000 yearly population of vaccinees and 20% response rate was updated in text to be 174 and 37, respectively.	Corrected the wrong numbers presented in the protocol. The correct numbers, as presented in Table 3, are 174 and 37, respectively.
Section 9.7.1 Primary analysis (Secondary endpoint)	Added "None" after "Secondary endpoint:". Deleted " • Knowledge and understanding of the key safety messages will be assessed through the percentage of vaccinees who provide desirable responses to the related questions on the key safety messages in the STAMARIL® PIL."	Shorten vaccinee questionnaire by removing secondary endpoint collected for secondary objective to decrease the time to completion.
Section 10.3.9 Compensation	Added the paragraph below at the end of the section. "Vaccinees will be offered an honorarium for the time they will spend while participating in this survey (which they may refuse). The time to complete the survey is estimated to be up to 5 minutes. The amount of the	The MAH plans to provide an honorarium to each vaccinee to motivate them to participate in the survey.

Annex 1 List of stand-alone	honorarium will be determined according to fair market value" Updated vaccinee questionnaire	Vaccinee questionnaire was
documents	being updated date	shortened on 31 May 2023 by removing Q1-Q4 designed for secondary objective.
Annex 6.1 Assessment of success (HCP questionnaire)	Objective "Awareness and Utilization" was split into two separate objectives, "Awareness (2 questions)" and "Utilization (7 questions)" Added "An HCP is considered successful for utilization when he/she utilizes either the UK (STAMARIL®) yellow fever pre-vaccination checklist or traveller checklist Success for utilization if ≥80% of HCPs are successful." Q11 was changed from "Complementary question" to "Question completed desirably [Answers: 1 or 2 are desirable]"	Split objective "Awareness and Utilization" for clarity: Awareness (Q6-Q7) and Utilization (Q8-Q14). Added assessment of success for "Utilization" objective. Q11 was incorrectly listed as complementary question. Corrected the error.
Annex 6.2 Assessment of success (Vaccinee	Deleted "Knowledge and Understanding (4 questions)" in	The MAH plans to shorten vaccinee questionnaire by
questionnaire)	Objectives and relevant contents related to this objective.	removing 4 questions designed for secondary objective to decrease the time to completion.

6 MILESTONES

Milestone	Planned date*
Submission of study protocol	April 2022 (actual)
Start of data collection	March 2023 (actual)
End of data collection	August-September 2023
Registration in the EU PAS register®	February 2023 (actual)
Final report of study results	January-February 2024

^{*}The timelines may vary depending on the MHRA approval and the recruitment (please refer to section 9.5.2).

31-May-2023 Version number: 3.0

7 RATIONALE AND BACKGROUND

Epidemiology of yellow fever and yellow fever vaccination

Yellow fever is an acute viral haemorrhagic illness caused by infection with the mosquito-borne yellow fever flavivirus. The main urban vector is the Aedes aegypti mosquito, which is found throughout the tropics. The presentation of yellow fever disease ranges in severity from a subclinical, non-specific viral illness to a sudden onset systemic disease including fever, jaundice, haemorrhage, and renal failure. Differences in yellow fever virus strains, as well as host immune factors that are not fully understood, are likely responsible for the range of clinical symptoms. Mortality can be as high as 50%.² Nowadays the disease occurs in the tropical regions of Africa and Central and South America.² Recent epidemics of yellow fever in Brazil and sub-Saharan Africa have become major public health concerns for resident populations as well as travellers.³ Accurate data on the burden of yellow fever are difficult to obtain because of the variable quality of disease surveillance and under reporting of the disease. Approximately 138,000 cases of yellow fever, including 78,000 deaths, occur annually, with the vast majority of reported cases and deaths (>90%) occurring in sub-Saharan Africa. Mosquitoes capable of transmitting yellow fever virus exist in regions where the disease does not presently occur and in regions, such as Asia, where yellow fever has never occurred. However, there is no risk of transmission in the United Kingdom (UK) from imported cases since the mosquito vectors are not present in the $UK^{1,2}$

Yellow fever vaccines have been available for about 80 years. The currently available yellow fever vaccines are live, attenuated preparations of the 17D strain of yellow fever virus. As of 2021, more than 600 million doses of 17D yellow fever vaccines have been used worldwide. In the UK, Sanofi Pasteur is the only marketing authorisation holder (MAH) for yellow fever vaccine (STAMARIL®). STAMARIL® is a live attenuated yellow fever 17D-204 strain vaccine which is prepared by culturing the virus in embryonated eggs.

Vaccination is recommended for people over 9 months of age who are travelling to or living in areas or countries with a risk of yellow fever transmission, as well as laboratory workers handling potentially infectious materials.⁶ Under the International Health Regulations (IHR) 2005 and to limit the spread of yellow fever, some countries require evidence of immunisation against yellow fever as a condition of entry, in the form of an International Certificate of Vaccination or Prophylaxis (ICVP). As a single dose of yellow fever vaccine is expected to confer life-long immunity, since July 2016 the ICVP is valid for the duration of the life of the person vaccinated.⁷

Vaccination guidelines

Current guidelines for the practice of travel medicine advise that the risk of travel-associated yellow fever disease, the country ICVP requirements, and the potential for serious adverse events (SAE) following yellow fever vaccination are considered as part of the individual risk assessment undertaken during a consultation at a travel clinic. Aside from the ICVP requirements, the IHR 2005 mandate that yellow fever vaccine can only be administered at yellow fever vaccination centres (YFVCs), designated by the health administration for the territory in which they are situated. These conditions are designed to ensure that individuals seeking yellow fever vaccine prior to travelling abroad have access to a formally registered YFVC, are provided with appropriate travel advice, and to help assure the quality and the safety of the procedures and

31-May-2023

Version number: 3.0

materials employed. Such centres have to be suitably qualified and follow a specific code of practice. In the UK, expert advice on travellers' yellow fever exposure risk, designation of centres and country ICVP requirements are available through the National Travel Health Network and Centre (NaTHNaC)⁸ and Public Health Scotland (PHS). Each YFVC has to nominate a Responsible Supervising Clinician, who must be a doctor, nurse or pharmacist and implements the Conditions of Designation and code of practice. The YFVCs are responsible under the Conditions of Designation, for the reporting and follow-up of all vaccine adverse events (AEs) to the Medicines and Healthcare products Regulatory Agency (MHRA), MAH (Sanofi Pasteur), NaTHNaC and Health Protection Scotland (HPS). The YFVCs are also required to submit an annual return of yellow fever vaccine use.

UK (STAMARIL®) yellow fever pre-vaccination checklist (for HCPs) (Annex 3)

Following two fatal adverse reactions to yellow fever vaccine in the UK in 2018-2019, due to unapproved use in both cases, the UK MHRA requested the MAH to add a standardised UK checklist, developed by MHRA (hereby referred to as 'UK (STAMARIL®) yellow fever prevaccination checklist' in this protocol), as part of local additional risk minimisation measures (aRMMs) in the STAMARIL® Risk Management Plan, to support the UK healthcare professionals (HCPs) in the benefit-risk assessment process. The objective of this checklist is to ensure compliance of HCPs from designated authorised YFVCs with indications, contraindications, warnings, and precautions of the yellow fever vaccine as per the Summary of Product Characteristics (SmPC) and to support the appropriate evaluation of individual travellers' risk-benefit balance. The most recent SmPC (dated 15 Feb 2021) details the required considerations of risk-benefit balance for individual travellers. The UK (STAMARIL®) yellow fever pre-vaccination checklist (Annex 3 has been published on 16 Nov 2021, on the MHRA Drug Safety Update website. ¹⁰

NaTHNaC/PHS yellow fever pre-vaccination checklist (Traveller's checklist) (Annex 4)

In the UK, NaTHNaC first published a yellow fever pre-vaccination checklist in July 2019, which was updated in January 2020 in accordance with the recommendations in the Commission on Human Medicine's Expert Working Group report. In September 2021, NaTHNaC and PHS produced a new version of the yellow fever pre-vaccination checklist (Annex 4). This checklist is a screening tool and is intended for vaccinees (travellers) to read and complete in advance of, or during, the travel health consultation; it is also commonly called the 'traveller's checklist'. Based on the Annual Return 2020 report published by NaTHNaC, >90% of YFVCs in England, Wales, and Northern Ireland used a traveller (vaccinee) checklist during the travel health consultation to assist with yellow fever vaccine risk assessment. The contents of this checklist are similar to that of the UK (STAMARIL®) yellow fever pre-vaccination checklist. Therefore, throughout this protocol, 'standardised yellow fever pre-vaccination checklist' refers to either or both these checklists (i.e. 'UK (STAMARIL®) yellow fever pre-vaccination checklist' and 'NaTHNaC/PHS yellow fever pre-vaccination checklist').

Furthermore, since a patient information leaflet (PIL) should be provided to each vaccinee by their HCPs during the vaccination consultation, therefore the STAMARIL® PIL was also amended in line with the revisions of the most recent SmPC (dated 15 Feb 2021). In view of the important role of a PIL in risk minimisation, the MAH was also asked to evaluate the effectiveness of the STAMARIL® PIL.

In this light, the present post-authorisation safety study (PASS) survey is designed to assess the effectiveness of the UK (STAMARIL®) yellow fever pre-vaccination checklist, among the qualified HCPs of designated authorised YFVCs. In addition, this survey will also assess the effectiveness of the STAMARIL® PIL among yellow fever vaccinees (or their parents/guardians if vaccinees are younger than 18 years old) in the UK.

8 RESEARCH QUESTION AND OBJECTIVES

The aim of the current study is to examine the effectiveness of the UK (STAMARIL®) yellow fever pre-vaccination checklist among the qualified HCPs of designated authorised YFVCs and of the STAMARIL® PIL among the yellow fever vaccinees in the UK by conducting a survey in this population.

The objectives and endpoints of this study are presented in **Table 1**.

Table 1 Objectives and endpoints

Objectives	Endpoints				
Primary objectives					
To measure: a. Awareness of the UK (STAMARIL®) yellow fever pre-vaccination checklist by qualified HCPs of designated authorised YFVCs in the UK.	a. The proportion of qualified HCPs who are aware of the UK (STAMARIL®) yellow fever pre-vaccination checklist. Success indicator for awareness: if ≥80% of qualified HCPs are successful (a qualified HCP is considered successful when he/she is aware of the UK (STAMARIL®) yellow fever pre-vaccination checklist).				
b. Utilisation of any standardised yellow fever pre-vaccination checklist(s) by qualified HCPs of designated authorised YFVCs in the UK.	 b. The proportion of qualified HCPs who frequently or always use one or both the standardised yellow fever prevaccination checklists. Success indicator for utilisation: if ≥80% of qualified HCPs are successful (a qualified HCP is considered successful when he/she frequently or always uses at least one of the standardised yellow fever pre-vaccination checklists). 				
c. Distribution of the STAMARIL® PIL by qualified HCPs of designated authorised YFVCs to yellow fever vaccinees in the UK.	c. The proportion of HCPs who frequently or always distribute the STAMARIL® PIL to yellow fever vaccinees in the UK. Success indicator for distribution of the STAMARIL® PIL by HCPs: if ≥80% of qualified HCPs are successful (a qualified HCP is considered successful when he/she is frequently or always distributes the STAMARIL® PIL).				

Property of the Sanofi Group - strictly confidential

31-May-2023

Version number: 3.0

To evaluate knowledge and understanding The proportion of qualified HCPs who of the key safety messages associated with provide desirable responses for each yellow fever vaccination in any question related to knowledge and standardised yellow fever pre-vaccination understanding of key safety messages. checklist(s) among qualified HCPs of Success indicator for knowledge and designated authorised YFVCs in the UK. understanding: If ≥80% of qualified HCPs are successful (a qualified HCP is considered successful when he/she provides at least 80% of desirable responses to questions related to knowledge and understanding). To verify the receipt of the STAMARIL® a. The proportion of yellow fever vaccinees who receive the STAMARIL® PIL by yellow fever vaccinees at the time they get vaccination consultation in the UK. PIL Success indicator for receipt of STAMARIL® PIL: If >80% of vaccinees are successful (a vaccinee is considered successful when he/she receives the STAMARIL® PIL). Secondary objective: None

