9.2.2.1 Inclusion criteria

The following criteria must be met in order to be enrolled in the study:

1. For HCPs: Qualified HCPs from designated authorised YFVCs who have provided consultation for yellow fever vaccine administration and/or administered yellow fever vaccines in the UK in the past 12 months and are willing to consent to participate in the

Property of the Sanofi Group - strictly confidential

31-May-2023

Version number: 3.0

- survey. A qualified HCP refers to the one who has undertaken the yellow fever training programme, sponsored by the NaTHNaC or PHS during the past 24 months.
- 2. For vaccinees: Individuals who receive yellow fever vaccine in the UK and are willing to consent (or their parents/guardians, if individuals are younger than 18 years old) to participate in the survey.

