9.5 STUDY SIZE

9.5.1 Determination of sample size

The sample size formula based on the normal approximation of the binomial distribution, for calculating the number of participants required for a proportion is as follows:

$$n = \frac{P \cdot (1-P) \cdot \left(Z_{1-\alpha/2}\right)^2}{e^2},$$

where P is the expected proportion, e is one half the desired width of the confidence interval (CI), and $Z_{1-\alpha/2}$ is the standard normal Z value corresponding to a cumulative probability of $1-\alpha/2$ (e.g., if α =.05 then Z = 1.96). The following table provides the margin of error for 95% CI based on various sample sizes and proportions of interest.

Table 2 Margin of error for 95% CI based on various sample sizes and proportions of interest

Margin of error for 95% CI (absolute precision)							
Proportion of interest	8%	7%	5.7%	5%	4%		
10%	54	71	106	139	216		
30%	126	165	248	323	504		
50%	150	196	295	384	600		
70%	126	165	248	323	504		
90%	54	71	106	139	216		

As P is not known in advance, we consider it to be 50%. Such a hypothesis yields the most conservative i.e. the largest, sample size.

Based on 2019 figures,²³ a minimum sample size of 200 HCPs (a 7% precision) and 150 vaccinees (a 8% precision) are targeted assuming an expected proportion of interest of 50%. If the proportion of interest is greater than 50% which may be predicted from other sources such as an Annual Return Report, the precision could be further increased with the same sample size, or the sample size could be further decreased with the same precision. For example, based on the Annual Return 2020 report published by NaTHNaC, 90.7% of YFVCs supplied the yellow fever vaccine PIL routinely to travellers receiving yellow fever vaccination. In this case, a sample size of 200 HCPs will achieve a precision below 4%. If a similar proportion of vaccinees (or parents/guardians of minor vaccinees) can also confirm receipt of yellow fever vaccine PIL, a sample size of 54 vaccinees will achieve an 8% precision in this case.

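### The utilisation indicator can be met with no use of the UK (STAMARIL) checklist under evaluation, and Annex 6 contradicts itself on whether the traveller's checklist counts

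*Protocol*

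**What the plan says.** Section 8 of the Protocol states the purpose: "The aim of the current study is to examine the effectiveness of the UK (STAMARIL®) yellow fever pre-vaccination checklist among the qualified HCPs". Section 7 likewise describes the survey as "designed to assess the effectiveness of the UK (STAMARIL®) yellow fever pre-vaccination checklist".

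For objective 1b, Table 1 sets the bar: "Success indicator for utilisation: if ≥80% of qualified HCPs are successful". An HCP is successful when "he/she frequently or always uses at least one of the standardised yellow fever pre-vaccination checklists". Section 9.7.1 and the rule text in Annex 6.1 also accept either checklist.

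Section 7 gives the history. The UK checklist appeared on 16 November 2021. The other tool is older: "NaTHNaC first published a yellow fever pre-vaccination checklist in July 2019". Citing the 2020 Annual Return, the section adds that ">90% of YFVCs in England, Wales, and Northern Ireland used a traveller (vaccinee) checklist during the travel health consultation". The reason given for treating the two tools together is that their contents are similar.

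Annex 6.1 asks about each tool separately: Q8 for the UK checklist and Q11 for the traveller's checklist, with answers 1 or 2 desirable for both. In the column on inclusion in the assessment of success, Q8 is marked Yes and Q11 is marked No.

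**The concern.** The measure that the regulator asked to have evaluated is the UK checklist. The only success criterion for using a checklist is one that an HCP can satisfy without ever opening it. Section 9.7.1 treats 80% on each primary outcome as suitable for judging whether a risk minimisation measure is effective, so a pass on utilisation is likely to be read as evidence that the UK checklist has been taken up. The indicator cannot carry that meaning, because the older tool was already in wide use.

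There is a second problem in the same place. If the Annex 6.1 inclusion column is followed literally, only Q8 decides utilisation, which is the opposite of what Table 1 says. Two analysts working from this Protocol could report different utilisation results from the same data.

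**Working it through.** **Inputs.** Minimum HCP sample 200, ideal goal 300 (Sections 4 and 9.5.1). Threshold 80%, applied to the observed proportion (Table 1). Traveller's checklist use in 2020 above 90% of centres (Section 7). Z = 1.96 (Section 9.5.1).

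**The plan's own figure.** Section 9.5.1 uses n = P(1−P)Z²/e². With P = 0.5 and e = 0.07: 0.25 × 3.8416 / 0.0049 = 196, as in Table 2. With e = 0.08 the result is 150.1 (stated 150) and with e = 0.057 it is 295.6 (stated 295). The sizing basis reproduces.

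**Chance of passing with zero UK-checklist use.** An HCP is then successful only through the traveller's checklist. Let p be the proportion who frequently or always use it. Passing needs at least 0.80 × 200 = 160 of 200, or 240 of 300. The exact binomial probability P(X ≥ 0.8n) is:

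| p (assumed) | n = 200 | n = 300 |
|---|---|---|
| 90% | >0.999 | >0.999 |
| 85% | 0.978 | 0.992 |
| 80% | 0.54 | 0.53 |
| 75% | 0.06 | 0.02 |

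At p = 90% the expected count is 180 of 200. Its Wilson 95% CI is 85.1% to 93.4%, wholly above the bar.

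**Why p is a range.** The 2020 figure counts centres, leaves out Scotland, and says only that a checklist was used. If 90% of HCPs are users and a share f of them are frequent or constant users, p = 0.9f. Reaching p = 80% needs f = 0.80/0.90 = 89%. With f = 95%, p = 85.5% and the chance of passing at n = 200 is 0.987. With f = 90%, p = 81% and it is 0.68. With f = 85%, p = 76.5% and it is 0.14.

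**How far the indicator moves with uptake.** Suppose 90% frequently or always use the traveller's checklist and a proportion u frequently or always use the UK one, independently. The pooled proportion is 1 − 0.1(1 − u): 90% at u = 0, 91% at u = 10%, 93% at u = 30% and 95% at u = 50%. Moving from no uptake to half of HCPs shifts the indicator by 5 points.

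**A UK-only rule.** If Q8 alone decided success, the probability of passing at zero uptake would be 0.

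**Annex 6.1 side by side.** The rule text makes either checklist sufficient. The inclusion column admits Q8 and excludes Q11. Section 9.7.1 requires all related questions to be answered desirably for every objective except knowledge. Taken together, the last two make Q8 alone decisive. Changing Q11 to Yes and nothing else would, under the same all-questions rule, require both checklists. Neither reading matches Table 1.

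**The case against.** The strongest defence is that nothing is hidden. Objective 1b is itself worded as use of any standardised checklist, so the endpoint matches its objective, and Section 7 gives a reason: the two tools have similar content. Awareness has a separate 80% criterion tied to the UK checklist alone. Section 9.7.1 has the proportion of desirable answers expressed for each question, so the Q8 result will appear in the report. The 2020 baseline is also looser than it looks, being at centre level, without frequency of use, and from before the September 2021 version of the traveller's checklist.

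All of this stands, and it limits the point. The mismatch is between the indicator and the study aim, not between objective and endpoint. It does not remove it. Similar content supports a pooled measure of screening practice; it does not show that the new tool is used. Awareness is not use. The per-question Q8 percentage has no criterion, and Section 9.7 takes it only over those who answered. The weaknesses of the baseline change how likely a pass at zero uptake is, not whether one is possible.

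A reader might go further and infer that the survey cannot reveal non-use of the UK checklist. The documents do not support that: Q8 is collected and reported, and Q9 and Q10 ask about reasons for non-use and difficulties.

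**Conclusion.** The point holds for utilisation. As defined in Table 1, Section 9.7.1 and the Annex 6.1 rule text, the indicator can be met with no use of the UK checklist and cannot isolate its contribution. Whether a pass at zero uptake is near certain or unlikely depends on an unknown: the probability at n = 200 runs from above 0.999 to 0.06 as frequent or constant traveller's-checklist use runs from 90% to 75%. The conflict over Q11 in Annex 6.1 needs no assumption.

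Two extensions are tempting and are not supported.

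- **PIL distribution.** Section 9.5.1 reports that "90.7% of YFVCs supplied the yellow fever vaccine PIL routinely to travellers receiving yellow fever vaccination", which is above the 80% bar. But the PIL is not pooled with another tool, the indicator measures attainment of a level and not improvement on 2020, and Section 9.7.1 openly calls the threshold subjective.
- **Knowledge.** Recent NaTHNaC or PHS training is an entry condition, so one might expect knowledge success to come from training. The Protocol gives no baseline score to show that 22 of 27 would be reached anyway. Objective 2 refers to messages in any checklist, and the description of responders is left to the SAP.

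**What to change.** 1. Keep the pooled indicator as objective 1b words it.
2. Reconcile Annex 6.1 and Section 9.7.1 with Table 1: mark Q11 as included, and state that for utilisation a desirable answer to either Q8 or Q11 is enough, as an exception to the all-questions rule.
3. Add a prespecified result for the UK checklist: the proportion answering 1 or 2 to Q8, with a Wilson 95% CI, read against the same 80% threshold. The denominator should be all eligible HCPs, with those unaware of the checklist or routed past Q8 counted as non-users. Section 9.8.1 mentions skip patterns and the questionnaire is a separate document, so without this rule the result could be restricted to HCPs who already know the tool.
4. State that conclusions about use of the UK checklist rest on awareness plus this result, and that the pooled indicator describes use of any checklist.

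The cost is small: Q6, Q7, Q8 and Q11 are already asked, so this needs a paragraph of text and one or two tables. There are two downsides. The UK-specific result may be less favourable than the pooled one. The criterion would also be added after data collection began in March 2023, which the report should say; Section 9.7.3 plans no early analysis.
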